1 PROTOCOL SYNOPSIS

| riance of Sponsor/Company. | ame of Product: | Name of Active Ingredient: |
|----------------------------|--|----------------------------|
| Covis Pharma B.V. Alv | lvesco [®] Inhalation Aerosol | ciclesonide |

Title of Study:

A Phase 3, Multicenter, Randomized, Double-Blind, Placebo-Controlled Study to Assess the Safety and Efficacy of Ciclesonide Metered-Dose Inhaler in Non-Hospitalized Patients 12 Years of Age and Older With Symptomatic COVID-19 Infection

Study Sites:

Up to 15 sites in the United States

| Protocol Number: | Development Phase: |
|------------------|--------------------|
| ALV-020-001 | Phase 3 |

Primary Objective:

The primary study objective is to assess whether treatment with ciclesonide metered-dose inhaler (MDI) plus standard supportive care results in improved time to alleviation of Coronavirus Disease 2019 (COVID-19)-related symptoms of cough, dyspnea, chills, feeling feverish, repeated shaking with chills, muscle pain, headache, sore throat, and new loss of taste or smell compared with placebo plus standard supportive care in non-hospitalized patients with symptomatic COVID-19 infection.

Secondary Objectives:

The secondary study objectives are:

- to assess whether treatment with ciclesonide MDI plus standard supportive care reduces the incidence of hospital admissions or death compared with placebo plus standard supportive care in non-hospitalized patients with symptomatic COVID-19 infection
- to assess whether treatment with ciclesonide MDI plus standard supportive care reduces all-cause mortality compared with placebo plus standard supportive care in non-hospitalized patients with symptomatic COVID-19 infection
- to assess whether treatment with ciclesonide MDI plus standard supportive care reduces COVID-19-related mortality compared with placebo plus standard supportive care in non-hospitalized patients with symptomatic COVID-19 infection
- to assess whether treatment with ciclesonide MDI plus standard supportive care reduces the incidence of subsequent emergency department visits or hospital admissions for reasons attributable to COVID-19 compared with placebo plus standard supportive care in non-hospitalized patients with symptomatic COVID-19 infection
- to assess whether treatment with ciclesonide MDI plus standard supportive care increases the percentage of patients with alleviation of COVID-19-related symptoms of cough, dyspnea, chills, feeling feverish, repeated shaking with chills, muscle pain, headache, sore throat, and new loss of taste or smell compared with placebo plus standard supportive care in non-hospitalized patients with symptomatic COVID-19 infection
- to assess whether treatment with ciclesonide MDI plus standard supportive care increases the time to hospital admission or death compared with placebo plus standard supportive care in non-hospitalized patients with symptomatic COVID-19 infection
- to assess the impact of treatment with ciclesonide MDI plus standard supportive care on oxygen saturation levels compared with placebo plus standard supportive care in non-hospitalized patients with symptomatic COVID-19 infection

| Name of Sponsor/Company: | Name of Product: | Name of Active Ingredient: |
|--------------------------|-----------------------------|----------------------------|
| Covis Pharma B.V. | Alvesco® Inhalation Aerosol | ciclesonide |

- to assess the impact of treatment with ciclesonide MDI plus standard supportive care on COVID-19 viral load compared with placebo plus standard supportive care in non-hospitalized patients with symptomatic COVID-19 infection
- to assess the safety of ciclesonide MDI plus standard supportive care compared with placebo plus standard supportive care in non-hospitalized patients with symptomatic COVID-19 infection

Methodology:

This is a multicenter, randomized, double-blind, placebo-controlled, parallel-group, efficacy and safety study of ciclesonide MDI for the treatment of symptomatic COVID-19 infection. Enrolled patients will be male and female adults and adolescents \geq 12 years of age with confirmed COVID-19 infection who are currently exhibiting symptoms of the disease and who are not currently hospitalized or under immediate consideration for hospitalization at the time of enrollment. The study will consist of an initial screening/enrollment/randomization visit, a 30-day treatment period, and a follow-up period. Following signature of the informed consent form, patients meeting inclusion/exclusion criteria will be randomly assigned (1:1) to treatment with ciclesonide MDI 320 µg twice daily (BID) (morning [AM] and evening [PM]) plus standard supportive care (hereafter referred to as the ciclesonide arm) or placebo MDI BID (AM and PM) plus standard supportive care (hereafter referred to as the placebo arm). During the initial screening/enrollment/randomization visit, patients will be instructed on how to self-administer a MDI and will be discharged home with a 30-day supply of investigational product (ie, either ciclesonide MDI or placebo MDI), standard supportive care, a pulse oximeter for at-home oxygen saturation level monitoring, and an electronic diary (eDiary). A nasopharyngeal sample for viral load analysis will also be obtained at the initial screening/enrollment/randomization visit. Patients will be instructed to record self-administration of investigational product and oxygen saturation levels in the eDiary. Prior to self-administration of the investigational product (ie, within 1 hour of administration). patients will also complete and record assessments in the eDiary of severity of COVID-19-related symptoms of cough, dyspnea, chills, and feeling feverish (based on a 4-point scale where 0 = absent, 1 = mild, 2 = moderate, and 3 = severe) and the presence/absence of COVID-19-related symptoms of repeated shaking with chills, muscle pain, headache, sore throat, and new loss of taste or smell. Qualified healthcare providers will contact patients on days 2, 4, 6, 8, 10, 12, 14, 21 ± 2 days, and 30 ± 2 days for a health status check, to collect adverse event and concomitant medication information, and to confirm/clarify information recorded in the eDiary. During these patient contacts, medical advice commensurate with standard of care for reported symptoms or adverse events will be provided. On day 30 (window of + 2 days), the patient will return to the study site for collection of a nasopharyngeal sample for viral load analysis and to return the eDiary and investigational product (ie, used and unused MDIs). Qualified healthcare providers will contact patients on day 37 ± 4 days and day 60 ± 7 days to collect follow-up safety and outcome data (the follow-up period).

Patients (or their representatives) will be asked to notify study personnel directly in the event they visit an emergency department or are hospitalized during their participation in the study.

Patient duration on study is expected to be approximately 60 days, including the

screening/enrollment/randomization visit, the 30-day treatment period and the subsequent follow-up period. In the event the patient requires hospitalization during the 30-day treatment period, the patient will discontinue investigational product and scheduled follow-up procedures but will continue to be followed for the outcome of hospitalization and ongoing adverse events.

An independent and appropriately constituted Data Monitoring Committee (DMC) will be organized for this study. A charter detailing the purpose of the committee as well as their roles and responsibilities will be put into place and will guide and direct their actions.

| Name of Sponsor/Company: | Name of Product. | Name of Active Ingredient: | | |
|---|--|---|--|--|
| Covis Pharma B.V. | Alvesco [®] Inhalation Aerosol | ciclesonide | | |
| Number of Patients | | | | |
| Approximately 400 patients (200 j | n each arm) will be randomized | | | |
| Approximately 400 patients (200 I | In cach ann) win oc randonized. | | | |
| Diagnosis and Main Criteria for | Inclusion: | | | |
| Inclusion Criteria | the study must meet all the follow | wing oritorio. | | |
| 1 Mala and formals adults and ad | a aaaanta > 12 yaars of ago | wing enterna. | | |
| 1. Male and lemale adults and ad | 212 years of age. | hin 72 hours prior to appellment | | |
| 2. Positive SARS-Cov-2 molecul | lized or under immediate consid | eration for hospitalization at the time | | |
| of enrollment. | | eration for hospitalization at the time | | |
| 4. Patient is currently experiencing | ng symptoms of fever, cough, an | d/or dyspnea. | | |
| 5. Patient has an oxygen saturation | on level > 93% . | - 1 | | |
| 6. Ability to show adequate use of | of MDI, including inhalation tech | nnique. | | |
| 7. Patient, parent/legal guardian, | or legally-authorized representat | tive must have signed a written | | |
| informed consent before admit | nistration of any study-specific p | procedures. | | |
| Exclusion Criteria | | | | |
| Patients meeting any of the follow | ing criteria are not eligible for pa | articipation in the study: | | |
| 1. Existence of any life-threateni of the investigator, makes the | Existence of any life-threatening co-morbidity or any other medical condition which, in the opinion of the investigator makes the patient unsuitable for inclusion | | | |
| 2. History of hypersensitivity to | ciclesonide. | | | |
| 3. Treatment with inhaled or intr enrollment/randomization visi | Treatment with inhaled or intranasal corticosteroids within 14 days of the screening/ enrollment/randomization visit. | | | |
| 4. Treatment with oral corticoste | roids within 90 days of the scree | ning/enrollment/randomization visit. | | |
| 5. Participation in any other clini screening/enrollment/randomi | cal trial or use of any investigatization visit. | onal agent within 30 days of the | | |
| 6. Currently receiving treatment | with hydroxychloroquine/chloro | quine. | | |
| 7. Patients with cystic fibrosis. | | | | |
| 8. Patients with idiopathic pulme | onary fibrosis. | | | |
| 9. Pregnancy (for females of chil | dbearing potential). | | | |
| Test Product, Dose, and Mode of | f Administration: | | | |
| Ciclesonide 160 µg/actuation MD | I, 320 μ g BID (2 actuations in the | e AM and 2 actuations in the PM), oral | | |
| inhalation | | | | |
| Reference Therapy, Dose, and M | lode of Administration: | | | |
| Placebo MDI, BID (2 actuations in the AM and 2 actuations in the PM), oral inhalation | | | | |
| Duration of Treatment: | | | | |

30 days

| Name of Sponsor/Company: | Name of Product: | Name of Active Ingredient: | | | |
|---|---|--|--|--|--|
| Covis Pharma B.V. | Alvesco [®] Inhalation Aerosol | ciclesonide | | | |
| Criteria for Evaluation: | | · | | | |
| Efficacy: | | | | | |
| Primary Efficacy Endpoint | | | | | |
| • Time to alleviation of COVID repeated shaking with chills, n defined as symptom-free for a day 30 | • Time to alleviation of COVID-19-related symptoms of cough, dyspnea, chills, feeling feverish, repeated shaking with chills, muscle pain, headache, sore throat, and new loss of taste or smell, defined as symptom-free for a continuous period of ≥ 24 hours (ie, ≥ 3 AM/PM assessments) by day 30 | | | | |
| Secondary Efficacy Endpoints | | | | | |
| • Percentage of patients with hos | pital admission or death by day | 30 | | | |
| • All-cause mortality by day 30 | | | | | |
| COVID-19-related mortality by | y day 30 | | | | |
| • Percentage of patients with subsequent emergency department visit or hospital admission for reasons attributable to COVID-19 by day 30 | | | | | |
| • Percentage of patients with alle feeling feverish, repeated shak taste or smell, defined as symp assessments) by day 7, by day | eviation of COVID-19-related sy ing with chills, muscle pain, hea otom-free for a continuous period 14, and by day 30 | Sumptoms of cough, dyspnea, chills, dache, sore throat, and new loss of d of \geq 24 hours (ie, \geq 3 AM/PM | | | |
| • Time to hospital admission or o | death | | | | |
| • Change from baseline in oxyge | en saturation levels | | | | |
| • Change from baseline in COVI | ID-19 viral load in nasopharynge | eal sample at day 30 | | | |
| Safety: Safety will be assessed bas | sed on adverse events. | | | | |

| Name of Sponsor/Company: | Name of Product: | Name of Active Ingredient: |
|--------------------------|-----------------------------|----------------------------|
| Covis Pharma B.V. | Alvesco® Inhalation Aerosol | ciclesonide |

Statistical Methods:

Efficacy

The primary efficacy variable is time to alleviation of COVID-19-related symptoms of cough, dyspnea, chills, feeling feverish, repeated shaking with chills, muscle pain, headache, sore throat, and new loss of taste or smell, defined as symptom-free for a continuous period of \geq 24 hours (ie, \geq 3 AM/PM assessments) by day 30. The primary analysis will be based on the intent-to-treat population (all randomized patients). To increase precision of treatment effect estimation and inference, a Cox proportional hazards model will be used to allow for inclusion of additional prespecified prognostic baseline covariates. The median time to event and 95% confidence intervals will be summarized by treatment arm, and Kaplan-Meier estimates of the survival curves will also be generated. The secondary efficacy endpoints of percentage of patients with hospital admission or death by day 30; all-cause mortality by day 30; COVID-19-related mortality by day 30; percentage of patients with subsequent emergency department visit or hospital admission for reasons attributable to COVID-19 by day 30; and percentage of patients with alleviation of COVID-19-related symptoms of cough, dyspnea, chills, feeling feverish, repeated shaking with chills, muscle pain, headache, sore throat, and new loss of taste or smell, defined as symptom-free for a continuous period of ≥ 24 hours (ie, ≥ 3 AM/PM assessments) by day 7, by day 14, and by day 30 will be analyzed using a logistic regression model. This will improve the precision of treatment effect estimation and inference by allowing for baseline covariate adjustments to be included in the model. Analysis of the secondary efficacy endpoint of time to hospital admission or death will be performed using the same method as that used for the primary efficacy endpoint. The secondary efficacy endpoint of change from baseline in oxygen saturation levels will be summarized descriptively at all timepoints captured in the eDiary. The secondary efficacy endpoint of change from baseline in COVID-19 viral load in nasopharyngeal sample at day 30 will be summarized descriptively.

Safety

The safety population will include all randomized patients who receive at least 1 dose of double-blind study medication. Safety will be evaluated by summarizing the incidence of adverse events. Comparative analyses will be done on adverse events of special interest (eg, oral candidiasis).

Interim Safety Review

The DMC will conduct a review of blinded safety data once 100 subjects have been enrolled. Details of the interim safety review will be described in detail in the DMC charter.

Sample Size and Power:

This study is designed to assess the efficacy and safety of ciclesonide MDI plus standard supportive care compared with placebo MDI plus standard supportive care. The primary endpoint is time to alleviation of COVID-19-related symptoms of cough, dyspnea, chills, feeling feverish, repeated shaking with chills, muscle pain, headache, sore throat, and new loss of taste or smell, defined as symptom-free for a continuous period of ≥ 24 hours (ie, ≥ 3 AM/PM assessments) by day 30. Assuming a median time to alleviation of 7 days for the ciclesonide arm and 11 days for the placebo arm (hazard ratio of approximately 1.58) with a total study duration of 30 days and a total of 201 events observed in the 2 arms combined, a sample size of approximately 232 patients (116 in each arm) is required to achieve 90% power at $\alpha = 0.05$ for the study. To account for an unknown drop-out rate in this patient population as well as other factors that may impact the overall power of the study, the planned sample size was increased to 400 patients (200 in each arm) for this study. Note that these are best estimates at this point as there is still much uncertainty regarding COVID-19.

TABLE OF CONTENTS

| D | escription | Page |
|---|---|------|
| 1 | Protocol Synopsis | 3 |
| 2 | List of Abbreviations and Definition of Terms | 11 |
| 3 | Introduction | 12 |
| | 3.1 Background Information on Coronavirus Disease 2019 (COVID-19) | 12 |
| | 3.2 Background Information on Ciclesonide and Rationale for Use in COVID-19 | 12 |
| | 3.3 Rationale for Dose Selection and Treatment Duration | 13 |
| | 3.4 Rationale for Subject Population | 14 |
| 4 | Study Objectives | 15 |
| | 4.1 Primary Objective | 15 |
| | 4.2 Secondary Objectives | 15 |
| | 4.3 Estimands | 16 |
| | 4.3.1 Primary Endpoint Estimand | 16 |
| | 4.3.2 Key Secondary Endpoint Estimand | 17 |
| 5 | Study Description | |
| | 5.1 Study Design | |
| | 5.2 Study Schedule | 19 |
| | 5.3 Study Visits and Procedures | 22 |
| | 5.3.1 Screening/Enrollment/Randomization Visit | 22 |
| | 5.3.2 Double-blind Treatment Period | 23 |
| | 5.3.3 Follow-up Period | |
| | 5.3.4 Early Termination Procedures | 24 |
| 6 | Patient Eligibility and Withdrawal Criteria | 25 |
| | 6.1 Number of Patients | 25 |
| | 6.2 Inclusion Criteria | 25 |

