4.3.2 Key Secondary Endpoint Estimand

The attributes of the estimand for the key secondary endpoint included in the multiplicity control procedure of this trial are:

- 1. Treatment regimens: ciclesonide and placebo
- 2. Populations of interest: patients meeting inclusion/exclusion criteria grouped according to randomized treatment assignment reflect the target population
- 3. Patient-level outcome: binary indicator of alleviation of COVID-19-related symptoms of cough, dyspnea, chills, feeling feverish, repeated shaking with chills, muscle pain, headache, sore throat, and new loss of taste or smell, defined as symptom-free for a continuous period of \geq 24 hours (ie, \geq 3 AM/PM assessments) by day 14
- 4. Intercurrent events: regardless of the use of rescue medications, protocol violations, or investigational product discontinuation
- 5. Population-level summary measure: difference in response probabilities between treatment regimens

The **treatment-policy strategy** for this estimand is the difference in probabilities of alleviation of COVID-19-related symptoms of cough, dyspnea, chills, feeling feverish, repeated shaking with chills, muscle pain, headache, sore throat, and new loss of taste or smell, defined as symptom-free for a continuous period of ≥ 24 hours (ie, ≥ 3 AM/PM assessments) by day 14 between those assigned to ciclesonide and those assigned to placebo, regardless of patient's use of rescue medications, protocol violations, or investigational product discontinuation. Therefore, for all patients in the ITT analysis set, all observed on-study data will be analyzed in accordance with the definition set forth above for intercurrent events.

Since death and hospitalization are not part of this key secondary endpoint patient level-outcome definition, a composite strategy will be used to handle these situations. If a patient dies or is hospitalized, then the value attributed in that scenario would be failure to achieve alleviation of COVID-19-related symptoms which ascribes the most unfavorable value.

Estimands for other secondary efficacy endpoints included in the multiplicity control procedure (section 10.7.3) will be described in the Statistical Analysis Plan (SAP).

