6.2 Inclusion Criteria

Patients eligible for enrollment in the study must meet all the following criteria:

- 1. Male and female adults and adolescents ≥ 12 years of age.
- 2. Positive SARS-CoV-2 molecular or antigen diagnostic test within 72 hours prior to enrollment.
- 3. Patient is not currently hospitalized or under immediate consideration for hospitalization at the time of enrollment.
- 4. Patient is currently experiencing symptoms of fever, cough, and/or dyspnea.
- 5. Patient has an oxygen saturation level > 93%.
- 6. Ability to show adequate use of MDI, including inhalation technique.
- 7. Patient, parent/legal guardian, or legally-authorized representative must have signed a written informed consent before administration of any study-specific procedures. In the event the patient is a minor under the age of 18, assent by the patient to participate in the study must also be obtained.

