7.1.2.3 Oxygen Saturation Levels

Oxygen saturation levels will be measured predose during the screening/enrollment/ randomization visit. During the 30-day treatment period, patients will be instructed to measure oxygen saturation levels (using the provided pulse oximeter) at a frequency of BID. The patient will record results of all assessments in the eDiary. The patient will be instructed to seek medical attention immediately should oxygen saturation levels fall to 93% or below.

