10.7.2 Secondary Efficacy Endpoints

The secondary efficacy endpoints of percentage of patients with hospital admission or death by day 30; all-cause mortality by day 30; COVID-19-related mortality by day 30; percentage of patients with subsequent emergency department visit or hospital admission for reasons attributable to COVID-19 by day 30; and percentage of patients with alleviation of COVID-19-related symptoms of cough, dyspnea, chills, feeling feverish, repeated shaking with chills, muscle pain, headache, sore throat, and new loss of taste or smell, defined as symptom-free for a continuous period of \geq 24 hours (ie, \geq 3 AM/PM assessments) by day 7, by day 14, and by day 30 will be analyzed using a logistic regression model. To improve the precisions on treatment effect estimation and inference, baseline covariate adjustments will be made for gender, age, race, and body mass index, as these are known COVID-19 risk factors. Analysis of the secondary efficacy endpoint of time to hospital admission or death will be performed using the same method as that used for the primary efficacy endpoint. The secondary efficacy endpoint of change from baseline in oxygen saturation levels will be summarized descriptively at all time points captured in the eDiary. The secondary efficacy endpoint of change from baseline in COVID-19 viral load in nasopharyngeal sample at day 30 will be summarized descriptively.

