10.7.3 Multiple Comparisons

In order to control the overall Type I error rate for the analyses of the planned primary and secondary endpoints, a fixed-sequence method will be utilized. Under this methodology, all endpoints will be ordered sequentially; testing will begin with the first endpoint (primary endpoint) at the full alpha level and continue through the sequence only until an endpoint is not statistically significant. The sequence of testing will be as follows:

- 1. Time to alleviation of COVID-19-related symptoms of cough, dyspnea, chills, feeling feverish, repeated shaking with chills, muscle pain, headache, sore throat, and new loss of taste or smell, defined as symptom-free for a continuous period of ≥ 24 hours (ie, ≥ 3 AM/PM assessments) by day 30
- Percentage of patients with alleviation of COVID-19-related symptoms of cough, dyspnea, chills, feeling feverish, repeated shaking with chills, muscle pain, headache, sore throat, and new loss of taste or smell, defined as symptom-free for a continuous period of ≥ 24 hours (ie, ≥ 3 AM/PM assessments) by day 14
- Percentage of patients with alleviation of COVID-19-related symptoms of cough, dyspnea, chills, feeling feverish, repeated shaking with chills, muscle pain, headache, sore throat, and new loss of taste or smell, defined as symptom-free for a continuous period of ≥ 24 hours (ie, ≥ 3 AM/PM assessments) by day 7
- Percentage of patients with alleviation of COVID-19-related symptoms of cough, dyspnea, chills, feeling feverish, repeated shaking with chills, muscle pain, headache, sore throat, and new loss of taste or smell, defined as symptom-free for a continuous period of ≥ 24 hours (ie, ≥ 3 AM/PM assessments) by day 30
- 5. Change from baseline in oxygen saturation levels at day 7
- 6. Change from baseline in COVID-19 viral load in nasopharyngeal sample at day 30

- 7. Percentage of patients with subsequent emergency department visit or hospital admission for reasons attributable to COVID-19 by day 30
- 8. Time to hospital admission or death
- 9. Percentage of patients with hospital admission or death by day 30
- 10. All-cause mortality by day 30
- 11. COVID-19-related mortality by day 30

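### SpO2 is never tied to a breathing condition and oxygen use is not recorded, so the > 93% entry criterion and the day 7 SpO2 comparison can be misread

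*Combined protocol and SAP*

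**What the plan says.** SpO2 has three roles in the protocol.

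- **Entry.** Section 6.2, criterion 5 (also in the synopsis): "Patient has an oxygen saturation level > 93" percent.
- **Baseline and home readings.** Section 7.1.2.3: "Oxygen saturation levels will be measured predose during the screening/enrollment/ randomization visit". For the treatment period, "patients will be instructed to measure oxygen saturation levels (using the provided pulse oximeter) at a frequency of BID", and "The patient will record results of all assessments in the eDiary".
- **Endpoint.** Section 10.7.3 places "Change from baseline in oxygen saturation levels at day 7" fifth of eleven steps in the fixed sequence. Section 10.7.2 says only that "change from baseline in oxygen saturation levels will be summarized descriptively at all time points captured in the eDiary".

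None of these places, nor Table 1 or sections 5.3.1 and 5.3.2, states the breathing condition. The synopsis instruction on the diary is "Patients will be instructed to record self-administration of investigational product and oxygen saturation levels in the eDiary"; with the symptom assessments added, the eDiary is described as holding dosing, symptoms and SpO2. The exclusions in 6.3 do not mention supplemental oxygen; the protocol names it only in a background case series in 3.2. Section 4.3.2 leaves the estimands of the remaining sequence endpoints to the SAP, and the available text has no SAP section in which to look for a rule.

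**The concern.** An SpO2 value can be interpreted only if one knows what the patient was breathing. Two uses of the number suffer without that.

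At entry, section 3.4 aims at mild to moderate disease. A reading of 95% on oxygen satisfies a bare threshold without showing that the patient is non-hypoxemic.

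At day 7, oxygen goes to patients who have deteriorated. If oxygen lifts the reading and nothing marks it, the record looks like recovery. This error is not random noise: it flatters whichever arm has more deterioration, so a real benefit of ciclesonide on oxygenation would be understated. In a fixed sequence, if steps 1 to 4 succeed, a failure at step 5 ends formal testing of steps 6 to 11, which include hospitalization and death.

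The data gap matters more than the missing rule. A SAP can supply a rule later, but it cannot reliably supply oxygen status at each reading if that was never collected.

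**Working it through.** **Can the situation arise under the protocol?** Taking the sections together:

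1. Patients reading 93% or below are told to seek medical attention (5.3.1, 7.1.2.3).
2. Supportive care follows the treating facility's standard; oxygen is neither named nor barred (3.3).
3. Hospitalization stops investigational product and scheduled procedures (5.1). Starting oxygen without admission has no such consequence.
4. Emergency department visits are counted alongside admissions as an outcome (7.1.1; step 7 in 10.7.3), so care without admission is foreseen.
5. Such a patient therefore continues twice-daily readings.

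**Could oxygen use be reconstructed?** Provider contacts fall on days 6 and 8, not day 7 (5.3.2). Section 8.8 collects concomitant medications at those contacts without naming oxygen. Neither links oxygen to a given reading.

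**The plan's own figures.** The documents state no SD, effect or power for SpO2. The only sizing figure is for the primary endpoint, and it reproduces with the Schoenfeld formula at a hazard ratio of 1.58, 90% power and two-sided 0.05 (sidedness is not stated): 4 x (1.960 + 1.282)^2 / (ln 1.58)^2 = 201 events. SpO2 does not enter it, so 201 events, 232 patients and the planned 400 are unaffected.

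**Illustration 1 (rates, changes and SD are assumptions; 200 per arm is from 10.1).** A share p of patients is on home oxygen at day 7. Their true room-air change is -6 points, their recorded change +1, and the SD is 2 points.

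- Contribution to the arm difference = (p ciclesonide - p placebo) x change.
- 1% versus 2%: true (-0.01)(-6) = +0.06; recorded (-0.01)(+1) = -0.01; error 0.07.
- 3% versus 6%: true (-0.03)(-6) = +0.18; recorded (-0.03)(+1) = -0.03; error 0.21.
- Standard error of the difference = 2 x sqrt(2/200) = 0.20.
- Error in standard errors: 0.07/0.20 = 0.35; 0.21/0.20 = 1.05.

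**Illustration 2 (same SD and n; a masked fall is recorded as no change).** Deterioration occurs in 10% of placebo and 5% of ciclesonide patients, with a 6-point fall. Power is for a two-sided 0.05 comparison of means, counting results in favour of ciclesonide.

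| Share of falls masked | Mean difference | Power |
|---|---|---|
| None | 0.05 x 6 = 0.30 | 0.32 |
| Half | 0.15 | 0.11 |
| All | 0 | 0.025 |

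With placebo deterioration of 5-15% (half that on ciclesonide) and falls of 4-6 points, power is 0.07-0.61 unmasked and 0.04-0.20 half-masked.

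**The case against.** The strongest reply is that the documents fix no outcome for these patients. No scoring rule is written, and the SAP could set one. Many patients who desaturate would be admitted, in which case the day 7 value is more likely to be missing than masked. The bias needs a patient who is given oxygen, is not admitted and keeps using the diary. This stands: a reader might infer that the plan scores such a patient as improved, but the text supports only that it can happen, where oxygen restores the reading and the raw value is used.

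There are also partial safeguards. Criterion 3 bars patients under immediate consideration for hospitalization, exclusion 1 allows investigator judgment, provider contacts are frequent, and worsening disease is an adverse event (9.1). These reduce the risk, but none is an oxygen rule or attaches oxygen status to a reading.

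A treatment-policy estimand, as in 4.3.1 and 4.3.2, would take readings on oxygen at face value by design. That is a legitimate choice for some questions, but those two estimands do not cover SpO2. Choosing it here would mean that the endpoint no longer separates recovery from oxygen therapy.

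Finally, a reader might infer from the negative recorded contributions that the arm difference changes sign. It need not. Values of -0.01 to -0.03 are 0.05 to 0.15 standard errors, and they describe one small subgroup, not the whole arm. On the same assumptions the unmasked contribution, 0.3 to 0.9 standard errors, would alone give only about 6-15% two-sided power, so masking is not the only reason step 5 might fail.

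**Conclusion.** The omission is real and appears wherever SpO2 is used. As written, criterion 5 does not reliably define a non-hypoxemic population, and an oxygen-raised reading at day 7 cannot be told apart from recovery. Any resulting bias runs toward the arm with more deterioration.

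Its size cannot be established from the documents. The 0.07-0.21 points (about 0.35 to 1 standard error) depend on assumed oxygen rates, changes and SD, and on an assumed halving of risk by ciclesonide. They show how attenuation would work; they do not show that the comparison reverses.

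The effect on the testing sequence is also conditional. It requires success at steps 1 to 4 and an actual test at step 5, whereas 10.7.2 provides only a descriptive summary. The point concerns eligibility and one secondary endpoint. It is a cheap improvement worth making before data are collected.

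**What to change.** 1. **Entry and baseline.** Add *on room air* to criterion 5 in section 6.2 and the synopsis, and state the same condition for the baseline reading in 7.1.2.3.
2. **Data capture.** Add one yes/no eDiary item to each SpO2 entry: supplemental oxygen in use at this reading. No patient is asked to come off oxygen for a reading.
3. **SAP.** Treat the start of oxygen as an intercurrent event for day 7 SpO2, with one prespecified rule that also covers patients hospitalized or dead by day 7. One option is a rank-based comparison placing death, hospitalization and oxygen use below all room-air values. Other rules are defensible if fixed before unblinding.
4. **Consistency.** Reconcile the descriptive-only analysis in 10.7.2 with the step 5 test in 10.7.3 by naming the test.

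Cost: a few words in the criterion and the baseline text, one diary item and a short SAP paragraph. The few patients already on oxygen become ineligible. No change to treatment or to the 93% alert is proposed.
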